#### 7.2.2 Protocol Deviations

Protocol deviations will be recorded separately from the clinical database. A blinded review of the deviation log, as well as a programmatic listing of protocol deviations to determine non-significant and significant protocol deviations, will be conducted prior to final database lock. All significant protocol deviations will be grouped by treatment group, AL002 40 and 60 mg/kg combined group, total AL002 group, and overall for the ARS. A by-participant data listing of all significant protocol deviations including categorization of deviations will be provided for the ARS as well.

## 7.3 Demographics and Baseline Characteristics

#### 7.3.1 Demographics, Baseline Characteristics, and Medical History

Demographics, baseline characteristics, social history, medical history, and medical and surgical treatment procedures will be summarized by treatment group, AL002 40 and 60 mg/kg combined group, total AL002 group, and overall. Demographics and baseline characteristics will be summarized for the ARS, FAS, and the Non-e4/e4 Set, respectively. Social history, medical history, and medical and surgical treatment procedures will be summarized for the ARS and the Non-e4/e4 Set, respectively. By-participant data listings will be presented for the ARS.

#### 7.3.2 Prior and Concomitant Medications

Prior and concomitant medications will be summarized for the Non-e4/e4 Set.

Prior medications will be summarized by ATC drug class Level 4 and preferred name using the number and percentage of participants for each treatment group, AL002 40 and 60 mg/kg combined group, total AL002 group, and overall.

Concomitant medications will be summarized by ATC drug class Level 4 and preferred name using the number and percentage of participants for each treatment group, AL002 40 and 60 mg/kg combined group, and total AL002 group.

A participant reporting the same medication more than once will be counted only once within each ATC drug class when calculating the number and percentage of participants who received that medication. Medications may appear under multiple ATC drug classes. Each summary will be ordered alphabetically

Protocol No. AL002-2 Last Revision Date: 12 Aug 2025

by ATC medical class and then by preferred name in descending overall frequency within each ATC medical class. For drugs with the same frequency, sorting will be done alphabetically.

All prior and concomitant medications (other than per-protocol study drugs) will be provided in a by-participant data listing sorted by randomized treatment, actual treatment, participant ID number and administration date in chronological order.

#### 7.4 Efficacy Analyses

The FAS will be used for all efficacy analyses, except for the analyses specified in Section 7.4.1.5, unless otherwise specified.

The primary estimand as described in Section 6.2.1.2 will be used for all efficacy analyses, except for the analyses specified in Section 7.4.1.5 which are based on the supportive estimand, and unless otherwise specified.

Missing data will be assumed missing at random (MAR) for all efficacy analyses, except for the analyses specified in Section 7.4.1.4, and unless otherwise specified. Sensitivity analysis to assess the impact of the missingness assumption will be performed using a Pattern Mixture Model (PMM) as described in Section 7.4.1.4.

For each continuous efficacy endpoint, the number of participants with efficacy outcomes, mean, SD, median, Q1, Q3, min, and max, at baseline and each scheduled post-baseline visit, along with CFB and PCFB to each scheduled post-baseline visit, will all be reported and accompany the estimates from the inferential statistical models. The same applies to subgroups specified in Section 7.4.3.

Unless otherwise indicated, all statistical tests will be 1-sided. However, 2-sided p-values will be reported for all tests. A significance level of 0.05 (1-sided) will be used for primary endpoint, with significance achieved if the 2-sided p-value is less than 0.10, and in the direction of indicating more efficacy for non-placebo than for placebo.

In the case of multiple values in an analysis visit window, data will be selected for analysis as described in Section 7.1.3.2, separately for each estimand.

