#### 5.3.2 Per-Protocol Analysis Set (PPS)

The PPS will consist of all participants in the FAS excluding participants who met either criterion:

- Any participant who did not receive at least 3 doses of study drug (i.e., total doses of study drug < 3),

- Any participant with major protocol deviations due to inclusion/exclusion criteria.

Protocol No. AL002-2 Last Revision Date: 12 Aug 2025

All analyses using the PPS will group participants according to the assigned treatment. This analysis set will be used for supplementary analyses of the primary efficacy endpoint.

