## 7.1.3 Selection of Data in the Event of Multiple Records in a Post-Baseline Analysis Visit Window

## 7.1.3.1 Efficacy Data

#### For non-composite efficacy endpoints:

If multiple valid, non-missing efficacy records exist in a post-baseline analysis visit window, records will be chosen based on the following rules if a single value is needed, unless otherwise specified:

- The record closest to the target day (in terms of days) for that visit will be selected.
- If there are multiple records that are equidistant from the target day (in terms of days), the later record will be selected.
- If there are multiple records on the same day and the chronological order (in terms of day and time) can be determined (e.g., more than one record with time known on the same day), the latest record will be selected.
- If there are multiple records on the same day and the chronological order cannot be determined (e.g., more than one record on the same day with time missing), the worst record will be selected.

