#### 7.4.1.3 Analyses of Supportive Estimand for Primary Efficacy Endpoint

The analyses described in Sections 7.4.1.1 (pMMRM), and 7.4.1.2 (MMRM) will be repeated with the supportive estimand for the primary efficacy endpoint, as described in Section 6.2.1.3.

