### 7.4.1.5 Supplementary Analyses on Per-Protocol Analysis Set (PPS)

Supplementary analyses on PPS will be performed as follows (Table 7-21):

Table 7-21. Supplementary Analyses on PPS

Primary Efficacy Endpoint	Timing	Methodology
CFB to all scheduled post-	Week 24, 48, 72, 96	pMMRM a
baseline visits in CDR-SB score		MMRM b

pMMRM = proportional Mixed-Effects Model for Repeated Measures, MMRM = Mixed-Effects Model for Repeated Measures.

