## 7.4.2 Analyses of Secondary Efficacy Endpoints

For the analysis of each of the secondary efficacy endpoints (Table 7-22), participants in the FAS who have a baseline value and at least one post-baseline value for the secondary endpoint being analyzed are included in the analysis.

Each of the secondary efficacy endpoints will be analyzed with pMMRM for proportional treatment effect  $(\theta)$  as described for the primary efficacy endpoint (Section 7.4.1.1). The same variables except that the baseline CDR-SB score will be replaced with the baseline for the secondary endpoint being analyzed will be included in the model.

In addition, each of the secondary efficacy endpoints will be analyzed with MMRM for CFB across all scheduled post-baseline visits and CFB to each scheduled post-baseline visit as described for the primary efficacy endpoint (Section 7.4.1.2). The same variables except that the baseline CDR-SB score will be replaced with the baseline for the secondary endpoint being analyzed will be included in the model. Also, the same analyses using the supportive estimand as described for the primary efficacy endpoint (Section 7.4.1.3) will be repeated for each of the secondary efficacy endpoints.

A forest plot of proportional treatment effect and 95% CIs from pMMRM will be drawn by treatment group for all efficacy endpoints including the primary and secondary efficacy endpoints. In the same plot, the point estimates of the proportional treatment effect will be displayed. Similarly, the forest plot of LSM difference at Week 96 and 95% CIs from MMRM will be drawn by treatment group for all efficacy endpoints. In the same plot, the point estimates of the LSM difference at Week 96 and the percent slowing of decline will be displayed side by side. The same forest plot for the LSM difference at "overall" from MMRM will be provided.

a same method as in Section 7.4.1.1

b same model as in Section 7.4.1.2

Protocol No. AL002-2 Last Revision Date: 12 Aug 2025

All secondary efficacy endpoints will be analyzed without adjustment for multiplicity and presented with nominal p-values.

Table 7-22. Analyses of Secondary Efficacy Endpoints

Secondary Endpoints	Methodology a
CFB in MMSE to Week 24, 48, 72, 96	pMMRM b , MMRM c
CFB in RBANS to Week 24, 48, 72, 96	pMMRM b , MMRM c
CFB in ADAS-Cog13 to Week 24, 48, 72, 96	pMMRM b , MMRM c

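### Two cross-references in SAP 7.4 point to the wrong sections: one puts the per-protocol analyses on the supportive estimand, the other sends duplicate efficacy records to the safety and biomarker rules

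*SAP*

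**What the plan says.** SAP 7.4 sets defaults for the efficacy analyses. The FAS is used except in 7.4.1.5. The primary estimand of 6.2.1.2 is used "except for the analyses specified in Section 7.4.1.5 which are based on the supportive estimand", unless otherwise specified. For several values in one visit window, "data will be selected for analysis as described in Section 7.1.3.2, separately for each estimand".

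The sections these sentences point to are:

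- **7.4.1.5** is the per-protocol section: "Supplementary analyses on PPS will be performed as follows", with pMMRM and MMRM on CDR-SB. It names no estimand. The footnotes to Table 7-21 take the methods from 7.4.1.1 ("same method as in Section 7.4.1.1") and 7.4.1.2.
- **7.4.1.3** holds the supportive-estimand work: the pMMRM and MMRM analyses "will be repeated with the supportive estimand for the primary efficacy endpoint, as described in Section 6.2.1.3".
- **5.3.2** removes from the PPS "Any participant who did not receive at least 3 doses of study drug" and anyone with a major eligibility deviation. Stopping drug after dose 3 does not exclude a participant.
- **6.2.1.2** (primary estimand) treats data as missing from 37 days after premature drug discontinuation.
- **6.2.1.3** defines two supportive estimands. One uses treatment policy for everything except death and keeps all on-study data. The other matches the primary estimand except for its population-level summary.
- **7.1.3.1** gives the duplicate-record rules for efficacy data; **7.1.3.2** gives those for safety and PD biomarker data.

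**The concern.** These sentences are operative rules, and SAP Section 1 gives the SAP precedence over the protocol. A programmer who follows 7.4 literally would put the PPS models on a supportive estimand. If that is the treatment-policy one, a per-protocol analysis would hold more off-drug data than the primary analysis it supplements.

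The PPS result would then differ from the primary result in two ways at once: who is analysed, and how drug discontinuation is handled. A difference between the two could not be assigned to eligibility or minimum dosing alone.

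Off-drug data will exist. Protocol 3.1.4 and 4.3.1 ask participants who stop drug to complete the remaining assessments. Early stopping is foreseeable too: Protocol 7.11.1.1 schedules MRI before doses 2, 3 and 4, and some findings in Table 7 of the protocol end treatment permanently.

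The second reference reaches further, because it covers every efficacy analysis including the primary. It points to rules that do not name efficacy data.

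**Working it through.** The plan states no figure to reproduce. The check sets the sections side by side and then works through the dosing calendar.

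**1. The estimand reference.** Three sentences in 7.4 carry exceptions.

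| Sentence in 7.4 | Section excepted | Content of that section | Fits? |
|---|---|---|---|
| FAS for all efficacy analyses | 7.4.1.5 | PPS analyses | Yes |
| Primary estimand for all efficacy analyses | 7.4.1.5 | PPS analyses | No; supportive estimand is in 7.4.1.3 |
| Missing at random | 7.4.1.4 | Pattern mixture model | Yes |

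The second row repeats the number of the first. SAP Section 9 lists a change to the PPS criteria but no change of estimand for the PPS. The SAP has a similar slip elsewhere: 7.5.6 and the notes to Tables 7-5, 7-6 and 7-8 cite 7.1.4.3 for predose and post-infusion handling, which is in 7.1.4.2.

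**2. What the literal reading would do.** Assume on-schedule dosing, the 37 days counted from the last dose, and the treatment-policy supportive estimand.

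- Dose *n* falls on Day 1 + 28(*n* − 1).
- Primary-estimand cut-off = day of last dose + 37.
- First scheduled post-baseline CDR-SB: Day 169 (SAP Table 7-1), with a ±5-day visit window, so Days 164 to 174.

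| Last dose | Day of dose | Cut-off day | Day 169 CDR-SB kept under primary estimand? |
|---|---|---|---|
| 3 | 57 | 94 | No |
| 4 | 85 | 122 | No |
| 5 | 113 | 150 | No |
| 6 | 141 | 178 | Yes |

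A participant whose last dose was the 3rd, 4th or 5th can be in the PPS, yet has no scheduled post-baseline CDR-SB under the primary estimand. Under treatment policy the same participant could contribute Weeks 24, 48, 72 and 96, all off drug. That is four visits with a 96-week planned period, or two (Weeks 24 and 48) with the 48-week minimum.

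Section 6.2.1.2 does not say which date the 37 days run from. If it were the first missed dose, 28 days later, the cut-offs for last doses 3, 4 and 5 would be Days 122, 150 and 178. Only those stopping after dose 3 or 4 would then lose the Day 169 visit.

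**3. The duplicate-record reference.**

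| Step | 7.1.3.1 (efficacy, non-composite) | 7.1.3.2 (continuous safety) |
|---|---|---|
| Several days in window | Closest to target day | Closest to target day |
| Equidistant | Later | Later |
| Same day, order known | "the latest record will be selected" | Average |
| Same day, order unknown | Worst | Average |

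Only the same-day rows differ. The PD biomarker branch of 7.1.3.2 averages all records in the window, but it is limited to biomarkers. Sections 6.2.2.5 and 6.2.2.6 (ADCOMS, modified iADRS) cite 7.1.3.1 correctly. Section 7.5 uses almost the same sentence with 7.1.3.2, where it is right because the data are safety data.

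**The case against.** The strongest reply is that these are evident numbering slips with little reach. The PPS section borrows the primary methods and names no estimand, whereas 7.4.1.3 invokes the supportive estimand expressly. The PPS analysis is supplementary and outside the fixed testing sequence. The wording that lets other text override the default protects 7.4.1.3, and 7.1.3.1 is plainly headed as the efficacy rule. All of this stands, and it limits the importance of the point. It does not remove it, because nothing in 7.4.1.5 overrides the estimand that 7.4 assigns to it.

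A deliberate choice cannot be excluded either: Protocol 8.2 says the PPS serves supportive efficacy analyses. But that describes the role of the set. Protocol 8.3.2.1 defines the supportive estimand without mentioning the PPS.

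A reader might infer three stronger things, which the documents do not support:

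- **That off-drug data are certain to enter the PPS analysis.** Of the two supportive estimands in 6.2.1.3, one keeps the hypothetical strategy and so the 37-day cut-off. Treatment policy is the likelier meaning, because 7.4.1.3 repeats both pMMRM and MMRM under the supportive estimand, but 7.4 does not say which is meant.
- **That a PPS difference could not be interpreted at all.** Section 7.4.1.3 runs the same models on the FAS under the supportive estimand. Comparing the PPS with that changes only the population.
- **That the dilution can be quantified.** One could take a 40% effect and let a share of participants stop halfway with half the benefit. The documents give no stopping rate for the PPS. Half the benefit would also describe only the final visit: with linear decline and a stop at Week 48, the effect is 40% at Weeks 24 and 48, about 27% at Week 72 (1 − (0.6 × 48 + 24)/72) and 20% at Week 96 (1 − (0.6 × 48 + 48)/96). The pMMRM fits one proportional effect across visits, with weights that depend on a covariance the documents do not give.

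**Conclusion.** Both cross-references are wrong and should be corrected.

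The estimand reference affects only the supplementary PPS analyses. The primary estimand, the primary analysis, the testing order and the sample size are unaffected by it. On the treatment-policy reading, the direct PPS-versus-primary comparison is lost, and the PPS models could include participants who have no scheduled post-baseline CDR-SB in the primary analysis. That illustration rests on on-schedule dosing and on counting the 37 days from the last dose. The effect on the estimate cannot be sized from the documents.

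The duplicate-record reference formally covers all efficacy analyses, including the primary. Against the continuous safety rule, it changes a value only when a participant has two assessments of the same scale on one day. The documents do not say how often that happens.

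**What to change.** In SAP 7.4:

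1. In the estimand sentence only, replace 7.4.1.5 with 7.4.1.3. Leave the FAS sentence as it is, since its reference to 7.4.1.5 is right.
2. State in 7.4.1.5 that the PPS analyses use the primary estimand. If a treatment-policy PPS analysis was intended, say so and name which supportive estimand of 6.2.1.3 applies.
3. In the sentence on multiple values in a visit window, replace 7.1.3.2 with 7.1.3.1.

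The cost is two section numbers and one sentence. No new data or analyses are needed.

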#### 7.4.1 Analyses of Primary Efficacy Endpoint

Participants in the FAS who have a baseline value and at least one post-baseline value for the primary endpoint are included in the analysis.

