3.3.4. Follow-Up Visits

When a randomized participant completes all study visits and procedures up to and including the final visit of their planned treatment period, an SFU visit will follow 8 weeks after this last treatment period visit, unless the participant enrolls in the AL002-LTE study. The end of a given participant's planned treatment period is defined by the TPTD as noted above. For participants who had paused dosing or who had prematurely discontinued dosing, the TPTD as noted above, will still define the end of their planned treatment period. The SFU visit will follow 8 weeks after the end of the planned treatment period for each participant, unless the participant enrolls in the AL002-LTE study. If a participant enrolls in the AL002-LTE study, an SFU visit is not required.

An EFU visit may or may not be required for a given participant, who has completed the planned treatment period and does not enroll in the AL002-LTE study. If a participant enrolls in the AL002-LTE study, an EFU visit is not required. For participants who do not enroll in the AL002-LTE study, an EFU visit is required 4 weeks prior to the SFU visit if the final COA and biomarker assessments were not completed within the defined time intervals as follows:

- An EFU is required if the last COA visit was done more than 12 weeks since the date the EFU visit would occur.
- An EFU visit is required if the last LP was done more than 12 weeks since the date the EFU visit would occur.
- An EFU is required if the last Amyloid PET or Tau PET was done more than 24 since the date the EFU visit would occur.

If the COA, LP, or PET biomarker assessments were not collected in the specified time period noted above, the participant will need to complete an EFU visit 4 weeks prior to the SFU visit.

An ET visit is performed only in cases where participation is permanently discontinued. If the participant withdraws or is discontinued from the study for any reason, the ET is completed 8 weeks after the last administered dose. Participants who complete an ET visit will not require a SFU visit, if the safety assessments were collected at a regularly scheduled study visit 8 weeks after the final dosing visit. Similarly, to the EFU visits for those who have completed the planned treatment period, the following efficacy and biomarkers are required as part of the ET visit if the following conditions are met:

COA visit was done more than 12 weeks since the date the ET visit would occur.

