#### 3.1.4 Treatment Administered

All participants in Part 1 and Part 2 will receive study treatment (placebo, 15 mg/kg AL002, 40 mg/kg AL002, or 60 mg/kg AL002). Study drug administration will begin on Day 1 visit and then will occur once every 4 weeks for the duration of the treatment period according to the Schedules of Assessments in the protocol.

In order to maintain the blind across all dose groups and allow step titration to the higher doses, the starting dose for each participant randomized to receive AL002 will be 15 mg/kg (or placebo) for the first study drug administration on Day 1 visit. For the second study drug administration, the dose will increase to 40 mg/kg for participants randomized to receive 40 mg/kg or 60 mg/kg, while doses in the other 2 groups will remain constant. For the third study drug administration, the dose will increase to 60 mg/kg for participants randomized to receive 60 mg/kg while doses in the other 3 groups will remain constant. The titration algorithm is provided in below Table 3-1.

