#### 3.5 Sample Size

The primary analysis model is a proportional mixed-model for repeated measurements (pMMRM) which estimates an average treatment effect over all the post-baseline visits. Our proposed model estimates the weighted average across the time-varying components. The model provides a clinically meaningful estimation of the treatment benefit averaged across the full duration of the clinical trial, rather than focusing on a single timepoint at the last visit, which may be a random high/low assessment.

To assess the power of the proposed pMMRM, a simulation experiment was conducted using the planned common close design with CDR-SB assessments at baseline, month 6, 12, 18 and 24. Data on the CDR-SB from clinical trials for AD, that are part of a master dataset (Kennedy, Cutter, et al., 2015; Kennedy, Wang, et al., 2015; G. Wang et al., 2015), was used as the basis for assumptions for the simulations. A total of 441 patients with a global baseline CDR score of 0.5 and 1.0 were selected from this master dataset and the mean and covariance matrix were estimated using a mixed-effects model for repeated measures (MMRM). The mean and covariance were then used in simulations to estimate the power of the study. The following table (Table 3-2) shows the power based on the planned primary analysis method (pMMRM), for different sample sizes per group and different treatment effect assumptions, under the common close design using a two-sided 10% significance level. Under the common close design, we have assumed that 22% (per visit), 27% (per visit), 44% (total) and 58% (total) of participants will be missing CDR-SB data at month 6, 12, 18 and 24, respectively, due to dropout and the common close nature of the study design. A total of 5000 simulations were run per scenario.

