#### 5.3.1 Full Analysis Set (FAS)

The FAS will consist of all participants who were randomized, received any amount of study drug, and are non-e4/e4. All analyses using the FAS will group participants according to the assigned treatment.

When change (or percent change) from baseline is assessed based on the FAS, participants will be included in the analysis only if the participants had both a baseline and a postbaseline measure.

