#### 6.2.1.2 Primary Estimand for Primary Efficacy Endpoint

- Treatment condition: while on study treatment regardless of other interventions.
- Target population: adult participants with early AD, excluding APOE e4/e4 participants as defined by the protocol inclusion/exclusion criteria.
- Primary endpoint: CFB in CDR-SB score to Weeks 24, 48, 72, and 96.
- Accounting for intercurrent events: a composite strategy will be used to handle intercurrent events as below:
  - Hypothetical strategy for handling premature study drug discontinuation for any reason (data will be considered missing after a participant prematurely discontinued study drug plus 37 days).
  - o Treatment policy strategy for handling all other intercurrent events.
- Population-level summary: the percent reduction relative to placebo decline (the proportional treatment effect), comparing each dose level to placebo.

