## 7.1.1.2.1 Efficacy Data

Efficacy endpoints are scheduled to be performed or collected at nominal visits per protocol: Screening, Week 25, Week 49, Week 73, Week 97, early termination (ET), and EFU (only collected if COA is not performed or collected within 12 weeks since the last COA collection). For the efficacy endpoints, assessments will be allocated to analysis visits using the analysis visit window intervals in which they fall in as specified in Table 7-1.

Efficacy data will be summarized based on the analysis visits (hereinafter may be referred to as "visit"), when applicable.

Table 7-1. Analysis Visit Windows for Efficacy Assessments

Nominal Visit per Protocol	Targeted Day of Nominal Visit (Based on Study Day)	Analysis Visit	Analysis Visit Window (Based on Study Day)
Scree			
Screening	-	Baseline b	~ 1
Treati	nent Phase	Baseline	≤1
Week 1 a	1		
Week 25	169	Week 24	[2, 253]
Week 49	337	Week 48	[254, 421]
Week 73	505	Week 72	[422, 589]
Week 97	673	Week 96	≥ 590

<sup>a COAs are scheduled to be performed/collected prior to dosing.

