#### 7.4.1.4 Sensitivity Analysis using Control-Based Pattern Mixture Model

To evaluate the impact of different patterns of missing CDR-SB values, a PMM with the primary estimand for the primary efficacy endpoint will be used in this study as a sensitivity analysis. PMMs have the advantages of allowing transparent and clinically interpretable formulations of the assumptions regarding unobserved data (Little & Rubin, 2019).

After the intermittent missing data are imputed, impute monotone missing at visits, up to the treatment period termination date (as defined in the protocol) plus 37 days, using a control-based PMM under the MNAR assumption. This is done because monotone missing data are presumed to be no longer on study drug, so could be treated as placebo control. Missing data will be imputed using sequential regression control-based pattern MI, where a separate regression model is estimated for imputation of each measurement at each visit.

The following sequential regression control-based pattern MI steps will be used:

- i. With each call to PROC MI, only one time-point will be imputed. Each regression model will include explanatory variables: post-baseline measurement, APOE e4 status (e4 carrier, non-e4 carrier), all previous measurements at each time point (up to the missing value time-point). Range restrictions implied to imputed CDR-SB score: 0-18. Imputed data will consist of 100 imputed datasets.
- ii. When imputing missing values for time-point *t*, the input dataset should include all placebo participants, but only those participants from AL002 that have values at time-point *t* missing (only those that need imputation at time-point *t*). Since participants from AL002 treatment groups with non-missing values at time-point *t* will not be included in the input dataset, they will not contribute to the estimation of an imputation model for time-point *t*. Imputation model will be estimated using placebo participants only. This way, missing values of participants from AL002 will be imputed based on the placebo participants' model.
- iii. Repeat step ii for all other time-points sequentially. Participants whose missing values were imputed with the previous PROC MI call will be included in the input dataset for the next call to PROC MI. Thus, data for time-point t, filled in during the last call, will be used for predictor variables in the next call to PROC MI (for time-point t + 1).

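### The control-based sensitivity analysis (SAP 7.4.1.4) inherits an inclusion rule that, on its natural reading, leaves out the earliest drug-stoppers

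*SAP*

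**What the plan says.** Under the primary estimand (SAP 6.2.1.2), premature stopping of study drug is handled by a hypothetical strategy: "data will be considered missing after a participant prematurely discontinued study drug plus 37 days". The SAP does not say whether the 37 days start at the last dose or at a recorded discontinuation date.

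On timing, SAP 7.1.1.2.1 states: "Efficacy endpoints are scheduled to be performed or collected at nominal visits per protocol: Screening, Week 25, Week 49, Week 73, Week 97". Table 7-1 puts the first post-baseline target at Day 169, and Protocol Table 9 allows ±5 days. SAP 3.1.4 starts dosing at the Day 1 visit, after which it "then will occur once every 4 weeks for the duration of the treatment period according to the Schedules of Assessments in the protocol". For a participant who leaves the study, Protocol 3.3.4 says "the ET is completed 8 weeks after the last administered dose".

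On inclusion, SAP 7.4.1, the parent of 7.4.1.1 to 7.4.1.5, states: "Participants in the FAS who have a baseline value and at least one post-baseline value for the primary endpoint are included in the analysis". SAP 5.3.1 adds, for any change-from-baseline assessment on the FAS, that "participants will be included in the analysis only if the participants had both a baseline and a postbaseline measure". The FAS itself needs only randomisation, a dose and a genotype other than e4/e4.

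SAP 7.4 assumes missing at random for the efficacy analyses other than 7.4.1.4. That section uses the primary estimand, fills intermittent gaps first, and then imputes monotone missing values from a model estimated on placebo participants. Its reason: "This is done because monotone missing data are presumed to be no longer on study drug, so could be treated as placebo control". Step i lists the predictors as a post-baseline measurement, APOE e4 status and the previous measurements; it does not name baseline CDR-SB.

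**The concern.** The inclusion rule costs a likelihood analysis under missing at random almost nothing, because a participant with no usable outcome carries almost no information about the treatment effect. A control-based analysis is different. It exists to ask what happens to the estimate if AL002 participants who are off drug are treated as placebo, and those who stopped drug earliest are the clearest members of that group. If they are filtered out before imputation, the analysis imputes only participants who stayed on drug long enough to have a usable Week 24 value.

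The structure of 7.4.1.4 makes this visible. Intermittent gaps are filled first, so a participant who is monotone-missing from Week 24 is by definition one with no post-baseline value. With the 7.4.1 rule applied after the 37-day cut, the Week 24 control-based step has no AL002 participant to act on.

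At stake is how demanding the only missing-not-at-random check is. It would be milder than its description suggests, and a result that survived it would look more robust than had been shown.

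**Working it through.** **The plan's own figures.** The planned size reproduces: 70 × 4 + 15 + 6 + 27 = 328, and 328 / 4 = 82 per group (SAP 3.5). The 83% power cannot be rebuilt, because the mean vector and covariance behind it are not given. It is not needed here.

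**Who has no usable scheduled value.** Inputs: doses every 4 weeks (Days 1, 29, 57, 85, 113, 141), the 37-day cut, and a Week 25 window of Day 164 to 174 (169 ± 5).

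- Last dose Week 13: 85 + 37 = Day 122, before Day 164, so lost.
- Last dose Week 17: 113 + 37 = Day 150, before Day 164, so lost.
- Last dose Week 21: 141 + 37 = Day 178, after Day 174, so kept.
- In continuous time the limit is 169 − 37 = Day 132, or 132 / 7 = 18.9 weeks.
- The early termination visit falls at last dose + 56 days, also outside last dose + 37.

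These results take the last dose as the start of the 37 days.

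**Effect of the omission.** Let Δ be the mean placebo change at a visit and θ the proportional effect among those included. Imputed from the placebo model at average covariates, the omitted share q has mean Δ. The arm mean is then

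(1 − q) × Δ(1 − θ) + q × Δ = Δ[1 − (1 − q)θ],

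so the estimate becomes (1 − q)θ.

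| q | θ = 40% | θ = 30% |
|---|---|---|
| 5% | 38.0% | 28.5% |
| 10% | 36.0% | 27.0% |
| 15% | 34.0% | 25.5% |
| 22% | 31.2% | 23.4% |

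**Where q could lie.** No figure in the documents gives it. SAP 3.5 assumes that, at months 6, 12, 18 and 24, "22% (per visit), 27% (per visit), 44% (total) and 58% (total) of participants will be" missing CDR-SB. The month 6 figure covers every cause, so 22% (0.22 × 70 = 15.4, or 0.22 × 82 = 18.0 per group) is an upper planning value. The 27 study discontinuations in SAP 3.5 (27 / 328 = 8.2%) are undated.

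**Cross-check.** The full sequence (placebo-model imputation, then a proportional model) was run on 200,000 participants per arm with true θ = 0.40. All other inputs were assumed: placebo changes 0.5, 1.1, 1.8, 2.5; SDs 1.2, 1.8, 2.4, 3.0; AR(1) correlation 0.7; later dropout 5%, 3%, 3%; and 22%, 17% and 61% of participants with two, three and four planned visits.

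| q | early stoppers omitted | included | ratio |
|---|---|---|---|
| 5% | 0.374 | 0.356 | 0.95 |
| 10% | 0.375 | 0.337 | 0.90 |
| 15% | 0.366 | 0.309 | 0.84 |
| 22% | 0.373 | 0.291 | 0.78 |

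The ratios follow 1 − q to within 0.01.

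**The case against.** The strongest reply is that the exclusion is an inference. SAP 7.4.1 does not say whether the rule is judged before or after the 37-day cut. The steps of 7.4.1.4 restate no restriction, take in all placebo participants and every AL002 participant missing at the visit, and end by analysing values that may be imputed or observed. A reading that leaves the Week 24 step empty could be held against itself. If the rule is applied to collected data, a participant who stopped early but was followed to Week 25 qualifies and is imputed throughout. This stands as an ambiguity. It does not remove the point: participants with no collected post-baseline CDR-SB are still left out, and two programmers could report different results from the same text.

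The start date also matters. If stopping is recorded at the missed Week 21 visit, 141 + 37 = Day 178 and the Week 25 value is kept. That moves the limit back one dosing interval: last dose Week 13, stop recorded at Week 17, 113 + 37 = Day 150, still lost at Week 25. An early termination CDR-SB could then qualify if the recorded stop is at least 56 − 37 = 19 days after the last dose. An unscheduled CDR-SB inside the cut would also map to Week 24, whose window is Day 2 to 253.

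A reader might infer that these participants vanish from every primary-endpoint analysis. They do not. Protocol 4.3.1 asks them to stay in follow-up, and SAP 7.4.1.3 repeats the pMMRM and MMRM under the supportive estimand of 6.2.1.3 with all on-study data kept. That is a direct use of their off-drug scores. It assumes missing at random, however, and cannot help those who also leave the study before Week 25, so it does not replace the control-based check.

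**Conclusion.** The point holds as a cheap improvement to the sensitivity analysis. The primary pMMRM and its test are unaffected. On the natural reading, with the rule applied after a 37-day cut that runs from the last dose, the only missing-not-at-random analysis omits participants last dosed at or before Week 17. On the alternative order it omits a smaller group, those with no collected post-baseline CDR-SB. Its estimate is too favourable by a factor of about 1 / (1 − q): 40% should read 38% at q = 5% and 31% at q = 22%, with q an assumption throughout.

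Two stronger statements are tempting and not supported. One is that this is the largest dropout pattern. Read as cumulative, the planned percentages rise by 22, 5, 17 and 14 points. If the first two are conditional on the preceding visit, the steps are 22.0, 21.1, 0.9 and 14.0. Either way they count missing CDR-SB for any reason, including the common close at later visits, and not drug stops.

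The other is that the omission must favour AL002 because early ARIA stops fall on active arms. That is plausible, but no counts by arm are given. Protocol Table 7 suspends dosing, with possible restart, for many ARIA findings. The Day 15 and Day 43 ARIA stops and the dose-limiting event rule apply to Part 1, about 40 participants. Protocol 1.3 places the serious and severe symptomatic cases in e4/e4 participants, who are outside the FAS.

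**What to change.** In SAP 7.4.1.4:

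- State that the requirement for a post-baseline value in 5.3.1 and 7.4.1 does not apply, and that the imputation input is all FAS participants with a baseline CDR-SB. The SAP's FAS definition already admits them.
- State that participants with no usable post-baseline value are imputed from the placebo model from Week 24 onward, in placebo as well as AL002 arms, within the time limit already set there.
- Correct the predictor list in step i to name baseline CDR-SB alongside APOE e4 status, so that a Week 24 imputation is defined.

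In SAP 6.2.1.2, state the date from which the 37 days run. Leave the primary pMMRM as it is.

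The cost is a few sentences before database lock and a wider imputation dataset. The price in results is a somewhat less favourable sensitivity estimate, by roughly the factor 1 − q.
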